**Sensitivity analyses**

Several sensitivity analyses will be performed as detailed in table below. Each time, descriptive analysis, evaluation of treatment effect (each dose versus placebo), evaluation of dose effect (1200 mg vs. 800 mg) will be performed as detailed above for main analysis.

Analysis population	Treatment group	Missing data replacement
FAS	Actual treatment received	Observed cases under treatment*
PP	Actual treatment received	Observed cases under treatment
EPP	Actual treatment received	Secondary imputation method

\* This analysis corresponds to analyses on completers (biopsy at week 24 performed, within maximum 14 days after last intake).

**Analysis by subgroups**

Descriptive analysis (number, % with its 95% confidence interval) will be performed in the FAS (primary imputation method) and among completers (Observed cases under treatment) as detailed in section 5.2.2.1 for the following subgroups of interest:

- Biopsy length at baseline ( $\leq 8$ ,  $>8$  mm)
- SAF-A score at baseline (A2-A3, A4)
- CRN-F score at baseline (F0-F1, F2-F3)
- NAS score at baseline ( $<6$ ,  $\geq 6$ )
- BMI at baseline (Obese, Non-obese)
- Metabolic syndrome at baseline (Yes, No)
- Insulin-resistance status at baseline (Yes, No)
- By site group No. 1 (Bulgaria, all other countries)
- By site group No. 2 (3 or less patients randomised and treated, from 4 to 9 patients randomised and treated, 10 or more patients randomised and treated)
- Sex (Male, Female)

#### 5.2.3.4 Resolution of NASH and Improvement of fibrosis by at least 1 stage

The endpoint will be a binary variable (responder / non responder) based on the CRN-I and CRN-B scores at Week 24 and the change in CRN-F score from Baseline to Week 24 (see section 4.5.4.1.10).

#### **Main analysis**

The population of analysis will be the FAS as described in section 4.3.3. The primary imputation method described in section 4.1.6.3 will be used for missing data replacement.

##### - Descriptive analysis

The number (% with its 95% confidence interval) of responders and non-responders at Week 24 will be summarized in a table using descriptive statistics by treatment group and diabetic status.

The reason for non-response (CRN-I score not equal to {0, 1},  $\pm$  CRN-B score not equal to 0,  $\pm$  No improvement of CRN-F score, No post-treatment biopsy available) will also be displayed.

##### - Evaluation of treatment effect (each dose versus placebo)

The same methodology as the one defined in the section 5.2.2.1 (paragraph ‘Evaluation of treatment effect (each dose versus placebo)’ ) will be implemented.

##### - Evaluation of dose effect (1200 mg vs. 800 mg)

Lanifibranor 1200 mg will be compared to lanifibranor 800 mg using a CMH test stratified on the diabetic status. The same methodology as the one defined in the section 5.2.2.4 (paragraph ‘Evaluation of dose effect (1200 mg vs. 800 mg)’ ) will be implemented.

##### - Dose-response relationship

Moreover, the dose-response relationship will be assessed on the FAS (Primary imputation method and Observed cases under treatment), and on the PP (Observed cases under treatment) according to method detailed in section 4.1.5 (Cochran-Armitage test using PROC LOGISTIC with adjustment on diabetic status).

#### **Sensitivity analyses**

Several sensitivity analyses will be performed as detailed in table below. Each time, descriptive analysis, evaluation of treatment effect treatment effect (each dose versus placebo), evaluation of dose effect (1200 mg vs. 800 mg) will be performed as detailed above for main analysis.

Analysis population	Treatment group	Missing data replacement
FAS	Actual treatment received	Observed cases under treatment*
PP	Actual treatment received	Observed cases under treatment
EPP	Actual treatment received	Secondary imputation method

\* This analysis corresponds to analyses on completers (biopsy at week 24 performed, within maximum 14 days after last intake).

**Analysis by subgroups**

Descriptive analysis (number, % with its 95% confidence interval) will be performed in the FAS (primary imputation method) and among completers (Observed cases under treatment) as detailed in section 5.2.2.1 for the following subgroups of interest:

- CRN-F score at baseline (F0-F1, F2-F3)
- NAS score at baseline (<6, ≥6)

***5.2.3.5 Resolution of NASH without worsening of fibrosis and NASH improvement***

The endpoint will be a binary variable (responder / non responder) based on the CRN-I and CRN-B scores at Week 24, the change in CRN-F score and CRN NAS score from Baseline to Week 24 (see section 4.5.4.1.11).

**Main analysis**

The population of analysis will be the FAS as described in section 4.3.3. The primary imputation method described in section 4.1.6.3 will be used for missing data replacement.

- Descriptive analysis

The number (% with its 95% confidence interval) of responders and non-responders at Week 24 will be summarized in a table using descriptive statistics by treatment group and diabetic status.

The reason for non-response (CRN-I score not equal to {0, 1}, ± CRN-B score not equal to 0, ± Worsening of CRN-F score, ± No decrease of 2 points of NAS score, No post-treatment biopsy available) will also be displayed.

- Evaluation of treatment effect (each dose versus placebo)

The same methodology as the one defined in the section 5.2.2.1 (paragraph ‘Evaluation of treatment effect (each dose versus placebo)’ ) will be implemented.

- Evaluation of dose effect (1200 mg vs. 800 mg)

Lanifibranor 1200 mg will be compared to lanifibranor 800 mg using a CMH test stratified on the diabetic status. The same methodology as the one defined in the section 5.2.2.4 (paragraph ‘Evaluation of dose effect (1200 mg vs. 800 mg)’ ) will be implemented.

**Sensitivity analyses**

Several sensitivity analyses will be performed as detailed in table below. Each time, descriptive analysis, evaluation of treatment effect treatment effect (each dose versus placebo), evaluation of dose effect (1200 mg vs. 800 mg) will be performed as detailed above for main analysis.

Analysis population	Treatment group	Missing data replacement
FAS	Actual treatment received	Observed cases under treatment*

PP	Actual treatment received	Observed cases under treatment
----	---------------------------	--------------------------------

\* This analysis corresponds to analyses on completers (biopsy at week 24 performed, within maximum 14 days after last intake).

### **Analysis by subgroups**

None

#### *5.2.3.6 Change in components Steatosis (CRN-S), Activity (SAF-A), Inflammation (CRN-I) and Ballooning (CRN-B)*

##### *5.2.3.6.1 Improvement*

The endpoints are the following components: CRN-S, CRN-I and CRN-B scores. For each component, the following variable will be considered based on the change from baseline to Week 24:

- Improvement of at least 1 point change of the component (Yes, No)

### **Descriptive analysis**

The population of analysis will be the FAS as described in section 4.3.3. The primary imputation method described in section 4.1.6.3 will be used for missing data replacement.

The number (% with its 95%CI) of improvement (Yes, No) at Week 24 will be summarized in a table using descriptive statistics by treatment group and diabetic status.

### **Evaluation of treatment effect (each dose versus placebo)**

The same methodology as the one defined in the section 5.2.2.1 (paragraph ‘Evaluation of treatment effect (each dose versus placebo)’ ) will be implemented.

### **Sensitivity analyses**

Several sensitivity analyses will be performed as detailed in table below. Each time, descriptive analysis will be performed as detailed above for main analysis.

Analysis population	Treatment group	Missing data replacement
FAS	Actual treatment received	Observed cases under treatment*
PP	Actual treatment received	Observed cases under treatment

\* This analysis corresponds to analyses on completers (biopsy at week 24 performed, within maximum 14 days after last intake).

##### *5.2.3.6.2 Change in components*

For each component (CRN-S, SAF-A, CRN-I and CRN-B scores), the following variables will be considered based on the change from baseline to Week 24 of:

- Absolute change of the component (quantitative variables)

- Change in the component (...Improvement of 2 points, Improvement of 1 point, No change, Worsening of 1 point, Worsening of 2 points...)
- Change in the component (Improvement of at least 1 point/No change/Worsening of at least 1 point)

### **Descriptive analysis**

The population of analysis will be the FAS as described in section 4.3.3. Only the observed cases under treatment will be analysed (see section 4.1.6.3).

Endpoint will be summarized at Week 24 in a table using descriptive statistics by treatment group and diabetic status.

### **Sensitivity analysis**

A single sensitivity analysis will be performed as detailed in table below. Each time, descriptive analysis will be performed as detailed above for main analysis.

Analysis population	Treatment group	Missing data replacement
PP	Actual treatment received	Observed cases under treatment

#### *5.2.3.7 Change in component Fibrosis of CRN score and modified Fibrosis Ishak*

##### *5.2.3.7.1 Improvement or No worsening*

The endpoints are the component CRN-F score and the modified Fibrosis Ishak score (modified ISHAK-F). For each score, the following variables will be considered based on the change from baseline to Week 24:

- Improvement of at least 1 point of the fibrosis score (Yes, No)
- No worsening of the fibrosis score (Yes, No)

### **Descriptive analysis**

The population of analysis will be the FAS as described in section 4.3.3. The primary imputation method described in section 4.1.6.3 will be used for missing data replacement.

The number (% with its 95% CI) of improvement (Yes, No) and no worsening (Yes, No) at Week 24 will be summarized in a table using descriptive statistics by treatment group and diabetic status.

### **Evaluation of treatment effect (each dose versus placebo)**

The same methodology as the one defined in the section 5.2.2.1 (paragraph ‘Evaluation of treatment effect (each dose versus placebo)’ ) will be implemented.

### **Sensitivity analyses**

Several sensitivity analyses will be performed as detailed in table below. Each time, descriptive analysis will be performed as detailed above for main analysis.

Analysis population	Treatment group	Missing data replacement
FAS	Actual treatment received	Observed cases under treatment*
PP	Actual treatment received	Observed cases under treatment

*\* This analysis corresponds to analyses on completers (biopsy at week 24 performed, within maximum 14 days after last intake).*

### **Analysis by subgroups**

Descriptive analysis will be performed in the FAS (primary imputation method) and among completers (Observed cases under treatment) for the following subgroups of interest:

- CRN-F score at baseline (F0-F1, F2-F3)

### 5.2.3.7.2 *Change in component*

For each fibrosis score (CRN-F and modified ISHAK-F scores), the following variables will be considered based on the change from baseline to Week 24 of:

- Absolute change of the score (quantitative variables)
- Change in the score (...Improvement of 2 points, Improvement of 1 point, No change, Worsening of 1 point, Worsening of 2 points...)
- Change in the score (Improvement of at least 1 point /No change/Worsening of at least 1 point)

### **Descriptive analysis**

The population of analysis will be the FAS as described in section 4.3.3. Only the observed cases under treatment will be analysed (see section 4.1.6.3).

Endpoint will be summarized at Week 24 in a table using descriptive statistics by treatment group and diabetic status.

### **Sensitivity analysis**

A single sensitivity analysis will be performed as detailed in table below. Each time, descriptive analysis will be performed as detailed above for main analysis.

Analysis population	Treatment group	Missing data replacement
PP	Actual treatment received	Observed cases under treatment

### **Analysis by subgroups**

Descriptive analysis regarding CRN-F will be performed in the FAS (Observed cases under treatment) for the following subgroups of interest:

- CRN-F score at baseline (F0-F1, F2-F3)

### 5.2.3.8 *Glucose metabolism*

#### **Main analysis**

The population of analysis will be the FAS as described in section 4.3.3. Only the observed cases under treatment will be analysed (see section 4.1.6.3).

Only fasting results will be considered for fasting glucose, insulin, C-peptid and HOMA index. HbA1c and fructosamide results will be considered regardless of the fasting status.

#### - Descriptive analysis

Fasting glucose and HbA1c assessed at Screening, Baseline, Week 4, Week 14, Week 24 and Week 28, as well as insulin, C-peptid, fructosamide and HOMA index assessed at Week 0 and Week 24, will be described over time using descriptive statistics by treatment group and diabetic status, in terms of:

- Raw values
- Absolute change from baseline

The 95% CI of the mean will also be provided.

- Status over time (Normal-Normal, Normal-Abnormal, Abnormal-Normal, Abnormal-Abnormal)

The 2 timepoints prior to first intake will have to be analysed: screening and baseline.

One graph will also be provided describing the raw values (with 95% CI) by treatment group over time (including screening values)

The HOMA index will also be described qualitatively over time using descriptive statistics by treatment group and diabetic status (HOMA < 3, ≥ 3).

- Absolute changes in HbA1c value will be described qualitatively over time using descriptive statistics by treatment group and diabetic status:
  - o Decrease of HbA1c (Decrease of 1%, No change (Change within ]-1% ; 1%[]), Increase ≥ 1%).
  - o Decrease of HbA1c (Decrease ≥ 0.5%, No change (Change within ]-0.5% ; 0.5%[]), Increase ≥ 0.5%)
- Evaluation of treatment effect (each dose versus placebo)

For fasting glucose, HbA1c, insulin and HOMA index, in order to evaluate each treatment dose versus placebo at week 24, a MMRM will be performed as detailed in section 4.1.5.

In order to take into account multiplicity of tests, the ascending Hochberg procedure will be applied (see section 4.1.5 for details).

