# 9. **Statistical Methods**

## 9.1 **Efficacy Assessments**

**Primary endpoint:** The primary efficacy endpoint will be a binary variable (responder / non-responder) based on the change from baseline to Week 24 of the SAF activity score. Responder is defined as a decrease from baseline to week 24 of at least 2 points of the SAF activity score combining hepatocellular inflammatory and ballooning without worsening of fibrosis. Any stage increase of fibrosis is considered fibrosis progression. The main question of interest is: “Does at

least one of the two doses increases the percentage of responders compared to placebo?”. The main comparison of interest is therefore each of the two verum groups versus placebo.

**Secondary endpoints:** The following changes from baseline to 24 weeks of treatment will be evaluated:

- Percent of patients with resolution of NASH (Steatosis with or without mild inflammation and no worsening of fibrosis) from baseline to end of treatment (week 24).
- Percent of patients with a change in components of SAF score from baseline to end of treatment (week 24):
  - Steatosis: -1 point
  - Lobular inflammation: -1 point
  - Ballooning: -1 point
- Percent of patients with at least 1-point improvement of fibrosis score on a 4-point scale (SAF) without worsening of NASH, defined as no increase for ballooning, inflammation, or steatosis, using the SAF scoring system, from baseline to end of treatment (week 24).
- Change in fibrosis score on a 4-points scale (SAF) and modified Ishak: - one point from baseline to end of treatment (week 24).
- Liver enzymes (ALT, AST,  $\gamma$ GT) change from baseline to end of treatment (week 24).
- Inflammatory markers (fibrinogen, hs-CRP, alpha2 macroglobulin and haptoglobin levels) change from baseline to end of treatment (week 24).
- Glucose metabolism (fasting glucose and insulin, HOMA index and, in subjects with T2DM, HbA1c) change from baseline to end of treatment (week 24).
- Main plasma lipids levels (TC, HDL-C, calculated LDL-C, TG and apoA1) change from baseline to end of treatment (week 24).
- Adiponectin change from baseline to end of treatment (week 24).

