The generalizability of the treatment effect across geographical area will be tested and the statistical strategy will be defined in the SAP once the sample size will be known by stratum and country and before the break of the randomization code.

There is no planned interim analysis for success. However, the DSMB may decide to perform some futility analyses in particular in case of safety concerns.

A series of sensitivity analyses will be performed to assess the robustness of results such as the use of a stratified test (country as a stratification factor), the use of other sets of patients (PP set, Evaluable set, Randomized set, completer set). In case of missing assessment at W24, the patient will be considered a non-responder. A responder is consequently a confirmed responder.

Secondary efficacy analyses:

- NASH improver rates in each dose will be compared to placebo using the Cochran Mantel Haenszel test stratified on diabetes.
- Percent of patients with resolution of NASH in each dose will be compared to placebo using the Cochran Mantel Haenszel test stratified on diabetes.
- Percent of patients with a change in components of SAF score in each dose will be compared to placebo using the Cochran Mantel Haenszel test stratified on diabetes.
- Percent of patients with at least 1-point improvement of fibrosis without worsening of NASH in each dose will be compared to placebo using the Cochran Mantel Haenszel test stratified on diabetes.

Planned exploratory analyses:

- Inflammatory markers (fibrinogen, hs-CRP, alpha2 macroglobulin and haptoglobin levels) change from baseline to end of treatment (week 24) will be compared using GLM with the diabetes and dose as covariates. A mixed model for repeated measures will also be used to compare the time course of the response of each treatment group.
- Transient Elastography and Controlled Attenuation Parameter change from baseline to end of treatment (week 24) will only be described.
- Glucose metabolism (fasting glucose and insulin, HOMA index and, in subjects with T2DM, HbA1c) change from baseline to end of treatment (week 24) will be compared using GLM with the diabetes

and dose as covariates. A mixed model for repeated measures will also be used to compare the time course of the response of each treatment group.

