- an Analysis of Covariance (**ANCOVA**) using the SAS MIXED procedure with the treatment and the diabetic status as covariates when specified

Or

- a Mixed Model for Repeated Measures (**MMRM**) when specified using the SAS MIXED procedure with:
  - a. The absolute change from baseline of the analysis variable as endpoint (MODEL statement of the MIXED procedure)
  - b. The time, treatment, the diabetic status, the interaction (treatment \* time) and the baseline value as fixed effects (MODEL statement of the MIXED procedure). Time, treatment and diabetic status being considered as categorical variables
  - c. A time repeated measure (REPEATED statement of the MIXED procedure) within each subject (SUBJECT = subject as option of the REPEATED

statement). An unstructured (type=UN) variance covariance matrix being used as option of the REPEATED statement

- d. The Kenward-Roger approximation to estimate denominator degrees of freedom and adjust standard errors (ddfm=kr option in MODEL statement)

In order to explore the validity of the model (and more accurately the assumption regarding independence, normality and constant variance of residuals), the following graphs will be provided: Q-Q plot of the residuals, distribution of residuals with its corresponding normal density estimate and scatterplot of residuals vs. predicted values.

With such models (ANCOVA, MMRM) different treatment effects will be evaluated:

- **Evaluation of treatment effect (Each dose vs. placebo) at week 24:** In order to evaluate each treatment dose versus placebo at week 24 the following contrasts of interest will be used:
  - o 800 mg/day vs. placebo: -1 for Placebo, 1 for 800 mg/day and 0 for 1200 mg/day
  - o 1200 mg/day vs. placebo: -1 for Placebo, 0 for 800 mg/day and 1 for 1200 mg/day.

In order to take into account multiplicity of tests, the ascending Hochberg procedure will be applied (see section 4.1.5).

- **Evaluation of dose effect (800 mg vs. 1200 mg) at week 24:** In order to evaluate the dose of 800 mg/day versus the dose of 1200 mg/day at week 24 the following contrast of interest will be used:
  - o 800 mg/day vs. 1200 mg/day: 0 for Placebo, -1 for 800 mg/day and 1 for 1200 mg/day
- **Time course of the response of each treatment group:** In order to evaluate the time course of the response of each dose (separately) at each time-point the following contrasts of interest will be used for each dose:

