Objectives/Endpoints	Type of analysis	Method of analysis	Population and imputation method
Glucose metabolism (fasting glucose, insulin, HOMA index, C-peptid, HbA1c and fructosamide)	Main analysis	Descriptive Treatment effect: MMRM or ANCOVA Time course: MMRM when possible	FAS – Observed Cases under treatment (considering only fasting values, when specified)
	Subgroups analysis (diabetic status) (HbA1c at for HbA1c)	Descriptive	FAS – Observed Cases under treatment (considering only fasting values, when specified)
Liver enzymes (ALT, AST, GGT, Alkaline Phosphatase, Total Bilirubin)	Main analysis	Descriptive Treatment effect: MMRM Time course: MMRM	FAS – Observed Cases under treatment
	Subgroup analysis (diabetic status)	Descriptive	FAS – Observed Cases under treatment
Plasma lipids levels (TC, HDL-C, LDL-C, TG, apoA1, FFA, Adiponectin, Leptin, APO B, APO C3 and FGF21)	Main analysis	Descriptive Treatment effect: MMRM or ANCOVA when specified Time course: MMRM when possible	FAS – Observed Cases under treatment considering only fasting values
	Subgroup analysis ; - diabetic status - statins at Baseline	Descriptive	FAS – Observed Cases under treatment considering only fasting values
Efficacy inflammatory markers (fibrinogen, hs- CRP, alpha2 macroglobulin, haptoglobin, IL-13, IL-17a, , IL-6, IL-1b, TNF-a, INFg)	Main analysis	Descriptive Treatment effect: ANCOVA when specified	FAS – Observed Cases under treatment

Objectives/Endpoints	Type of analysis	Method of analysis	Population and imputation method
Efficacy fibrosis markers (TIMP-1, TIMP-2, Hyaluronic acid, P3NP, NFS, FIB-4 score, ELF score, MACK-3, FIBC3, ABC3D, Cytokeratin M30, Cytokeratin M65, Liver iron content, MMP2, MMP9, Pro-C3)	Main analysis	Descriptive Treatment effect: ANCOVA when specified	FAS – Observed Cases under treatment
	Exploratory analysis	Cross-tabulation with the CRN-F score (F0-F1, F2-F3) when specified	FAS – Observed Cases under treatment
Efficacy chemistry markers (Plasma Iron, Transferrin, Ferritin)	Main analysis	Descriptive	FAS – Observed Cases under treatment

Subgroups of interest are :

(1)

- Biopsy length ( $\leq 8$ ,  $>8$  mm)
- SAF-A at Baseline (A2-A3, A4)
- CRN-F at Baseline (F0-F1, F2-F3)
- NAS score at baseline ( $<6$ ,  $\geq 6$ )
- BMI at Baseline (Obese, Non-Obese)Metabolic syndrome at Baseline (Yes, No)
- Insulin-resistance status at Baseline (Yes, No)
- Sex (Male, Female)

(2)

- NAS score at baseline ( $<6$ ,  $\geq 6$ )

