**Sensitivity analysis**

None

**Analysis by subgroups** (descriptive analysis only)

- By diabetic status (Yes, No) for fasting glucose, insulin, C-peptid, HOMA index, fructosamide and HbA1c
- By HbA1c at baseline ( $\leq 6.5\%$ ,  $>6.5\%$ ) for HbA1c

*5.2.3.9 Liver enzymes*

The following table describes for each parameter the collection time and the type of analyses to be done.

Parameter	Collection time	Main analyses (see section 5.2.3.8 describing the methodology)	Sensitivity analyses	Subgroup analyses
ALT	Screening, Baseline, weeks 4, 14, 24 and 28	Descriptive analysis Treatment effect ( each dose versus placebo ) Time course of the response of each treatment group	None	By diabetic status (Yes, No)
AST	Screening, Baseline, weeks 4, 14, 24 and 28	Descriptive analysis Treatment effect ( each dose versus placebo ) Time course of the response of each treatment group	None	By diabetic status (Yes, No)
GGT	Screening, Baseline, weeks 4, 14, 24 and 28	Descriptive analysis Treatment effect ( each dose versus placebo ) Time course of the response of each treatment group	None	By diabetic status (Yes, No)
Alkaline Phosphatase	Screening, Baseline, weeks 4, 14, 24 and 28	Descriptive analysis	None	By diabetic status (Yes, No)
Total Bilirubin	Screening, Baseline, weeks 4, 14, 24 and 28	Descriptive analysis	None	By diabetic status (Yes, No)

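### The protocol defines its HbA1c endpoint in patients with type 2 diabetes, but the SAP tests HbA1c only in the whole FAS and gives diabetic patients no between-arm estimate or test

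*SAP*

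**What the plan says.** **Protocol 5.0.** Section 9.1 lists, among the secondary endpoints, week-24 change in "fasting glucose and insulin, HOMA index and, in subjects with T2DM, HbA1c". The synopsis has the same restriction. Section 9.7.4 repeats it and plans inference: "in subjects with T2DM, HbA1c) change from baseline to end of treatment (week 24) will be compared using GLM", with diabetes and dose as covariates, plus a mixed model for the time course. That text stands under the planned exploratory analyses.

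**SAP 5.2.3.8.** For glucose metabolism, "The population of analysis will be the FAS as described in section 4.3.3", using observed cases under treatment. The between-arm analysis reads: "For fasting glucose, HbA1c, insulin and HOMA index, in order to evaluate each treatment dose versus placebo at week 24", an MMRM is fitted, with Hochberg over the two doses. The MMRM in SAP 4.1.5 has as fixed effects "The time, treatment, the diabetic status, the interaction" of treatment with time, and the baseline value. There is no treatment-by-diabetes interaction.

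**Diabetic patients.** The subgroup list in SAP 5.2.3.8 is marked as descriptive and includes "By diabetic status (Yes, No) for fasting glucose, insulin, C-peptid, HOMA index, fructosamide and HbA1c". The table in SAP 5.2.1 agrees: its row "Subgroups analysis (diabetic status) (HbA1c at for HbA1c") has Descriptive as the method. No sensitivity analysis is planned. The list of modifications from the protocol in SAP 4.6 does not mention a change of population for HbA1c.

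**The concern.** The protocol asks whether each dose changes HbA1c in patients with T2DM. The SAP's only test asks whether each dose changes HbA1c on average over diabetic and non-diabetic patients. Adjusting for diabetic status removes a difference in level between the strata; it does not estimate the treatment effect within one of them.

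For diabetic patients, the SAP output is the mean change per arm with its own 95% CI, plus categories of change. There is no difference between arms, no interval for a difference and no p-value. For binary endpoints the SAP does more: section 5.2.2.1 plans a Breslow-Day test and gives odds ratios and risk ratios in each diabetes stratum whatever its result. HbA1c, the one glucose measure whose definition depends on diabetes, has no equivalent.

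At stake is whether a protocol-listed secondary endpoint gets a formal answer in the population for which it was defined.

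**Working it through.** The documents state no sample size, effect or SD for HbA1c, so there is no planned figure to reproduce. The main check is of the text.

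**Step 1: is the FAS model in practice a T2DM model?** It would be if HbA1c were measured only in T2DM. The schedules in both documents do attach HbA1c to subjects with T2DM. Against that, the laboratory panel in the protocol synopsis and Protocol Table 8 list HbA1c without restriction, and SAP 5.2.3.8 describes it for diabetic status Yes and No. With T2DM-only collection the No group would be empty. Collection in all patients is the better reading, so the two populations differ.

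**Step 2: does any planned contrast give the T2DM effect?** No. The only interaction in the model is treatment by time, so each dose has one week-24 contrast common to both strata.

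**Step 3: what does the FAS contrast estimate?** Randomisation is 1:1:1 within diabetes strata, so to a good approximation

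FAS effect = f × (T2DM effect) + (1 − f) × (non-diabetic effect),

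where f is the T2DM share. f is not given; 30% to 60% is assumed. As a share of the T2DM effect:

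| Non-diabetic effect relative to T2DM effect | f = 30% | f = 60% |
|---|---|---|
| 0 | 0.30 | 0.60 |
| 0.5 | 0.30 + 0.70 × 0.5 = 0.65 | 0.60 + 0.40 × 0.5 = 0.80 |
| 1 | 1.00 | 1.00 |

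**Step 4: what can a T2DM-only test detect?** SAP 3.5 reports 247 randomised, about 82 per arm. With f = 30% to 60% that is about 25 to 49 T2DM patients per arm. The detectable difference at 80% power is (z for alpha + z for power) × √(2/n) in SD units. At two-sided alpha 0.025 this is (2.241 + 0.842) × √(2/24.7) = 0.88 SD down to (2.241 + 0.842) × √(2/49.4) = 0.62 SD, before missing data.

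**Step 5: power of the two tests.** All inputs are assumptions except the planned 75 per arm and the first Hochberg level of 0.025: f = 40%, T2DM effect −0.4, SDs 0.7 (T2DM) and 0.25 (non-diabetic).

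- T2DM only: n = 30 per arm; SE = 0.7 × √(2/30) = 0.181; 0.4/0.181 = 2.21; power = Φ(2.21 − 2.24) ≈ 49%.
- FAS: pooled SD = √(0.4 × 0.49 + 0.6 × 0.0625) = 0.483; SE = 0.483 × √(2/75) = 0.0789.
  - Non-diabetic effect 0: FAS effect 0.4 × 0.4 = 0.16; 0.16/0.0789 = 2.03; power ≈ 42%.
  - Non-diabetic effect −0.1: FAS effect 0.16 + 0.6 × 0.1 = 0.22; 0.22/0.0789 = 2.79; power ≈ 71%.

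Power can therefore favour either test. The reason for the T2DM analysis is the question it answers, not power.

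**The case against.** **The protocol's analysis text is loose.** Section 9.7.4 names diabetes as a covariate for the whole glucose group, and that covariate is constant in a T2DM-only HbA1c model. The SAP follows this wording, and the protocol lets SAP clarifications prevail unless they cause major inconsistencies. This stands in part. But the same sentence also covers glucose, insulin and HOMA, where the covariate makes sense, and it states the T2DM restriction on HbA1c. The SAP does not present the wider population as a clarification.

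**The protocol version differs.** The SAP is written against version 5.1; the protocol supplied is 5.0. A reader might infer an undeclared departure. The documents show only that SAP 4.6 is silent and that version 5.0 has the restriction; the wording of 5.1 cannot be checked.

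**T2DM results will be visible.** This stands. It would be wrong to infer that diabetic patients go unreported: their means and CIs by arm are planned. What is missing is the comparison between arms.

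**Two stronger statistical readings fail.** A reader might infer that the FAS test understates the drug's effect on HbA1c. That needs a smaller effect in non-diabetic patients, which no document states. A reader might also argue that unequal variances in the two strata invalidate the FAS contrast. With allocation stratified on diabetes the arms have similar mixes, so unequal variance does not by itself bias the contrast.

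**The stakes are modest.** HbA1c is one of many secondary parameters, with no multiplicity control across parameters. This stands, and it limits the weight of the point.

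**Conclusion.** The mismatch is real. Protocol 5.0 restricts HbA1c to T2DM in three places and plans a between-arm comparison; the SAP tests HbA1c only in the whole FAS, with a model that yields no T2DM contrast. As written, the endpoint has no formal inference in its defined population.

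The numerical consequence cannot be fixed from the documents. It runs from no dilution, if the effect is the same in both strata, to an FAS estimate of 30% to 60% of the T2DM effect, if non-diabetic patients do not respond and the T2DM share is 30% to 60%. The conclusion assumes that HbA1c is collected in all patients, which is the better reading although the schedules suggest otherwise. It should be corrected because the remedy is cheap and uses data already collected. The primary analysis and its conclusion are untouched.

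**What to change.** In SAP 5.2.3.8, add for HbA1c the MMRM of each dose versus placebo at week 24, with Hochberg over the two doses, in patients with T2DM at baseline. Drop the diabetic-status term, which is constant there. Alternatively, add treatment-by-diabetes (by time) terms to the FAS model and report the T2DM contrast; in that case let the residual covariance differ by diabetic status, because a pooled one would misstate the standard error of that contrast if the variances differ.

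Name this as the analysis of the protocol endpoint, keep the whole-FAS model as supportive, and record both populations in SAP 4.6. State in the same place whether HbA1c is collected in all patients.

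The cost is one extra model and a few lines of SAP text, a smaller n and a wider interval. Power is lower than for the FAS test if non-diabetic patients also respond: about 49% against 71% under the assumptions in the last step of the working, and about 49% against 42% if they do not. No new data are needed, since diabetic status is already the stratification factor.
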